Patients with known or suspected brain metastases at screening shall have a CT/MRI of the brain prior to starting study drug. These patients shall be followed up on study with repeated CT/MRI assessment, using the same frequency as RECIST assessments. The same modality for CT/MRI shall be used for a patient throughout the study. Brain metastases will be assessed as nontarget lesions (NTLs).

If the investigator is in doubt as to whether progression has occurred, particularly with response to NTLs or the appearance of a new lesion, it is advisable to continue treatment until the next scheduled assessment or sooner if clinically indicated and reassess the patient's status. If repeat scans confirm progression, then the date of the initial scan shall be declared as the date of progression.

For those patients who have not progressed at the time of study drug discontinuation, tumor assessments should continue every 8 weeks from the previous, regularly scheduled scan until

disease progression or study completion. If the patient does not plan to return for subsequent post-treatment scans and has not had a scan within the prior 4 weeks, perform tumor assessment at the Discontinuation visit.

The same method of assessment (CT or MRI) shall be used to characterize tumors at screening and at all follow-up assessments. If positron emission tomography (PET) is used, it shall also be accompanied by spiral CT or MRI.

RECIST Version 1.1 - Blinded Independent Central Review Assessment

The BICR of radiological imagining data will be carried out using RECIST version 1.1. All radiological scans for all subjects (including those at unscheduled visits, or outside visit windows) will be provided to the BICR. Prior radiotherapy reports for subjects (at baseline) and information on biopsied lesions will also be provided to the BICR as appropriate. Further details of the BICR will be documented in the Blinded Independent Review Charter.

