11.3. Discontinuation of Study Drug

Study drug(s) shall be discontinued if any of the following events occur during the study:

- A patient suffers an AE that, in the judgment of the investigator, sponsor, or medical monitor, presents an unacceptable risk to the patient (see Section 8.3.3.2 for additional details).
- General or specific changes in the patient's condition (eg, a significant intercurrent illness or complication) that, in the judgment of the investigator, are unacceptable for further administration of study drug
- Occurrence of pregnancy
- Significant noncompliance with protocol requirements
- The sponsor or legal representative of the sponsor requests the patient to withdraw
- Patient has radiographically documented or clinically determined disease progression, with the exception of patients in Part 2 that crossover from osimertinib alone to G1T38 + osimertinib at the time of disease progression.

In the event of study drug discontinuation, patients shall be strongly encouraged to complete all scheduled assessments; the Post-Treatment Visit; and the Survival Follow-up Phase of the study. A patient who discontinues study drug for reasons other than PD shall have a CT or MRI scan at the Post-Treatment Visit, if they have not had a scan within the prior 4 weeks and the patient does not plan to return for subsequent post-treatment scans.

When discontinuation is due to a SAE or a Grade 3 or 4 toxicity considered to be related to study drug, the investigator shall follow the event until resolution, return to baseline, or it is deemed that further recovery is unlikely.

In the event a patient discontinues due to an AE or pregnancy, the investigator shall notify the medical monitor or PPD Safety Services by telephone within 24 hours of study drug discontinuation.

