12.3.2. Efficacy Endpoints

Antitumor efficacy endpoints include the following:

- Best overall response (BOR) according to RECIST v1.1
- Objective response (OR) (CR or PR) according to RECIST v1.1
- Duration of OR, and time to first objective response according to RECIST v1.1
- Clinical benefit rate (CBR) according to RECIST v1.1
- Progression-free survival (PFS) according to RECIST v1.1
- Overall survival (OS)

BOR will be determined using visit responses up until the last evaluable overall visit response prior to or on the date of (i) radiographic or clinical disease progression; (ii) withdrawal of consent to obtain scans; or (iii) receiving subsequent anticancer therapy, whichever is earlier. At each tumor assessment visit, an overall time point response by RECIST 1.1 will be determined programmatically - using the information from target lesions, NTLs, and new lesions.

For patients who progress and subsequently have a response, then the best objective response is only derived from assessments up to and including the time of the progression (ie, it will not include the response after the patient has progressed).

When the minimum interval for confirmation of CR and PR is not satisfied or if there are no confirmatory scans for CR and PR for a patient, then 2 ways of assigning BOR will be implemented in the analysis. In the primary analysis, BOR will be assigned as SD according to RECIST 1.1, which requires confirmation of CR and PR; in the other method, 2 or more response categories will be added as unconfirmed CR and unconfirmed PR. Both ways of assigning BOR will be implemented in the analysis.

Objective response will be derived as No/Yes (0/1) variable. Patients with a BOR of confirmed CR or PR will be assigned "Yes". Patients not having a BOR of confirmed CR or PR will be assigned "No." Hence, objective response rate (ORR) is defined as the proportion of patients with objective response being "Yes."

Clinical benefit rate (CBR) is defined as the proportion of patients with a BOR of confirmed CR or confirmed PR or SD at the 8 week (end of Cycle 2) or later assessment. A patient will

be considered to have a SD for 8 weeks or longer if a SD response is recorded at 8 weeks or later from first date of study drug administration.

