4.1 Efficacy Endpoints

4.1.1 General Consideration for Tumor Response Assessment

Progressive disease (PD) and tumor response status will be derived per RECIST v1.1 based on tumor assessment data entered into the EDC by investigators.

The methods used at baseline (i.e., the screening visit) for assessment of tumor burden (computed tomography [CT] or magnetic resonance imaging [MRI] scans of chest and abdomen [including liver and adrenal glands]) must be used at each subsequent follow-up assessment. The baseline assessment shall be performed within 21 days of treatment start. CT or MRI scans obtained prior to informed consent will not need to be repeated if performed within 21 days prior to the first dose of study drug. Subsequent assessments are to be performed every 8 weeks relative to Cycle 1 Day 1 until the date of (i) radiographic disease progression as defined by RECIST 1.1 (Eisenhauer et al, 2009); or (ii) withdrawal of consent to obtain scans; or (iii) receiving subsequent anti-cancer therapy, whichever is earlier. After 18 months of treatment, subsequent tumor assessments shall be performed every 12 weeks (\pm 1 week).

At each tumor assessment visit, an overall visit response by RECIST will be determined programmatically - using the information from investigator's measurement of target lesions (TL), non-target lesions (NTLs) and new lesions collected on electronic case report form (eCRF). The overall response at each time point is also assessed by the investigators and is collected on eCRF.

Antitumor efficacy endpoints include the following based on RECIST v1.1

- Best Overall Response (BOR)
- Objective response rate (ORR) (complete response [CR] or partial response [PR])
- Duration of objective response (DOR), and time to first objective response
- DCR at week 8 (complete response [CR] or partial response [PR] or stable disease [SD])
- PFS

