At each tumor assessment visit, an overall time point response of CR, PR, SD, Non-CR/Non-PD, PD or NE by RECIST Version 1.1 will be determined programmatically, using the information from TL, NTLs, and new lesions.

Best Overall Response

Best overall response is defined as the best overall response across all time points. BOR will be determined using overall time point responses up until the last evaluable time point response prior to or on the date of (i) radiographic disease progression as defined by RECIST 1.1 (Eisenhauer et al, 2009); or (ii) withdrawal of consent; or (iii) receiving subsequent anti-cancer therapy, whichever is earlier.

A patient's BOR will be determined based on [Table 4](#). For data-driven scenarios which may not be covered by [Table 4](#), the BOR will be reviewed and determined by the medical advisors and statisticians prior to database lock.

For patients who progress and subsequently have a response, then the best objective response is only derived from assessments up to and including the time of the progression (i.e., it will not include the response after the patient has progressed).

According to tumor assessment schedule (Table 9-1 in protocol), the first post-baseline disease assessment will be obtained at the end of Cycle 2 (study day 56) with a window ± 7 days (study day 49 through day 63). Therefore, a patient will be considered to have BOR of SD or Non-CR/Non-PD if a SD or Non-CR/Non-PD time point response is recorded no earlier than Day 49 since first G1T38 daily continuous dosing (Cycle 1 Day 1).

When the minimum interval (i.e., 4 weeks) for confirmation of CR and PR is not satisfied or if there are no confirmatory scans for CR and PR for a patient, then two ways of assigning BOR will be implemented in the analysis ([Table 4](#)). In the primary analysis, BOR will be assigned as stable disease (SD) according to RECIST 1.1, provided minimum 49 days SD duration criteria met, otherwise BOR will be assigned as PD or NE depends on the response of the confirmation assessment. In the other method, two more response categories will be added as unconfirmed CR and unconfirmed PR.

Table 4 Best Overall Response When Confirmation of CR and PR are Required [a]

First TPR[b]	Subsequent TPR	Best overall response (confirmed CR and PR)	Best Overall Response*(Confirmed and unconfirmed CR and PR)
CR	CR	CR	CR
CR	PR	SD [c] or PD	Unconfirmed CR
CR	SD or Non-CR/Non-PD	SD or Non-CR/Non-PD [c] or PD	Unconfirmed CR

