CR	PD	SD or Non-CR/Non-PD [c] or PD	Unconfirmed CR
CR	NE or NA	SD or Non-CR/Non-PD[d] or NE	Unconfirmed CR
PR	CR	PR	Unconfirmed CR
PR	PR	PR	PR
PR	SD	SD	Unconfirmed PR
PR	PD	SD [c] or PD	Unconfirmed PR
PR	NE or NA	SD [d] or NE	Unconfirmed PR
NE	NE	NE	NE

CR = complete response, PR= partial response, SD = stable disease, PD = progressive disease, NE = not evaluable, NA = not available; ORR = Objective Response Rate, TPR = time point response.

- The minimum interval for confirmation of CR and PR is 4 weeks (28 days).
- First appearance of CR or PR per RECIST 1.1.
- Best response will be SD or Non-CR/Non-PD if the first time point overall response is on or after 49 days on study. Otherwise, the best response will be PD.
- Best response will be SD or Non-CR/Non-PD if the first time point overall response is on or after 49 days on study. Otherwise, the best response will be NE.

A best overall response of SD or Non-CR/Non-PD can only be made after the patient has tumor assessment on day 49 (counted from first once-daily dosing date, Cycle 1 Day 1) or later. Otherwise, any tumor assessment indicated stable disease before this time period will have a best response of NE unless PD is identified. If a PD is indicated for the first TPR, then the BOR will be PD regardless of subsequent TPRs.

Subsequent documentation of a CR may provide confirmation of a previously identified CR even with an intervening not evaluable (NE) (e.g., CR NE CR). Subsequent documentation of a PR may provide confirmation of a previously identified PR even with an intervening NE or SD (e.g., PR NE PR or PR SD PR). However, only one (1) intervening NE or SD will be allowed between PRs for confirmation. Note: in the following scenario, PR SD NE PR, the second PR is not a confirmed PR.

Objective Response Rate

Objective response rate will be calculated based on either (1) confirmed tumor responses or (2) confirmed and unconfirmed tumor responses

Objective response will be derived as No/Yes (0/1) variable. For confirmed objective response (OR_{CONFIRMED}), patients with a BOR of confirmed CR or PR will be assigned “Yes”. Patients not having a BOR of confirmed CR or PR will be assigned “No.” Hence, ORR is defined as the proportion of patients with confirmed objective response being “Yes” among the analysis set.

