Unconfirmed objective response (OR_{UNCONFIRMED}) will be derived as No/Yes (0/1) variable. Patients with a BOR of confirmed CR, confirmed PR, unconfirmed CR or unconfirmed PR will be assigned “Yes”. All patients with other BOR values will be assigned “No”. Hence, ORR_{UNCONFIRMED} is defined as the proportion of patients with OR_{UNCONFIRMED} being “Yes”.

Disease Control Rate at Week 8

Disease control rate (DCR) at Week 8 is defined as the proportion of patients with a BOR of confirmed CR or confirmed PR or SD or Non-CR/Non-PD at 8 weeks. For patients without measurable lesions at baseline, a BOR of Non-CR/Non-PD will be considered achieving disease control.

Duration of Objective Response

Duration of objective response (DOR) is the time between first objective response of CR or PR and the first date that progressive disease (PD) is objectively documented or death. Patients who experienced an objective response but who do not experience objective PD or death at the time of analysis will be censored at the last adequate assessment date. Adequate assessment is defined as there is sufficient data to evaluate a patient’s disease status. DOR will be calculated only for patients who experience a confirmed objective response.

Time to First Objective Response

Time to first objective response is the time from first dose of once-daily dosing of G1T38 (Cycle 1 Day 1) to first objective response of CR or PR. This variable will be calculated only for patients who experience a confirmed objective response.

Progression-free Survival

Progressive disease (PD) is defined as radiographical determined disease progression based on the criteria by RECIST Version 1.1, which is also referred to as “documented disease progression” in the SAP. PD status is derived from the radiographical assessments by investigators that have been entered to the EDC. A PFS event is defined as a PD event or a death due to any cause.

PFS is defined as the time (months) from start date of continuous daily of G1T38 (i.e. Cycle 1 Day 1) to the date of the first documented PFS event, and the time from start date of continuous daily of G1T38 to the censoring date for those patients that did not experience a PFS event. That is, PFS is calculated as (date of PFS event or censoring – start date of continuous daily of G1T38 + 1)/

G1 Therapeutics, Inc.
Clinical Study Protocol G1T38-03
Statistical Analysis Plan

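### The SAP drops clinical progression from the protocol's best-overall-response cut-off without declaring it, so ORR and DCR can only rise or stay the same against the protocol definition

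*SAP*

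**What the plan says.** Protocol 12.3.2, which governs Part 1 efficacy, uses visit responses up to the last evaluable one on or before the earliest of three dates: "i) radiographic or clinical disease progression; (ii) withdrawal of consent to obtain scans; or (iii) receiving subsequent anticancer therapy, whichever is earlier".

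SAP 4.1.2.1 (Best Overall Response) has the same structure, but limb one is "i) radiographic disease progression as defined by RECIST 1.1". The SAP's PFS text defines progression in the same way: "Progressive disease (PD) is defined as radiographical determined disease progression based on the criteria by RECIST Version 1.1".

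Other provisions bear on the point:

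- Protocol 11.3 makes clinical progression a reason to stop study drug: "Patient has radiographically documented or clinically determined disease progression".
- Protocol 10.1 says that, for patients not yet progressed when drug stops, "tumor assessments should continue every 8 weeks from the previous, regularly scheduled scan until" progression or study completion. Table 9-1 also marks a tumor assessment at Discontinuation.
- SAP 4.1.1 states: "Subsequent assessments are to be performed every 8 weeks relative to Cycle 1 Day 1 until the date of" radiographic progression, withdrawal of consent to scans, or new therapy. Clinical progression does not end the schedule.
- The SAP sets a floor for stable disease: "A best overall response of SD or Non-CR/Non-PD can only be made after the patient has tumor assessment on day 49" or later. It requires 28 days between scans to confirm CR or PR.
- SAP Section 7 lists departures from the protocol. The BOR cut-off is not among them. The entry replacing CBR by DCR says the definition is unchanged.

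**The concern.** DCR and ORR are both computed from BOR, so the date that closes the BOR window decides which scans can make a patient a success. The protocol closes it when the investigator judges that the disease has progressed clinically. The SAP leaves it open past that date until one of the other events occurs. A patient taken off drug for clinical progression can then be counted as disease control, or more rarely as a confirmed responder, on a scan that the protocol would not use.

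A secondary endpoint would then depart from its protocol definition in the favourable direction, and a reader relying on Section 7 would be told that DCR is what the protocol called CBR. Part 1 has no control arm in which the same shift could offset it.

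**Working it through.** The documents give no figure to reproduce. The check is a comparison of texts, some worked patients, and the weight of one patient.

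**1. Does other SAP text restore the missing limb?**

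- The sentence limiting BOR to assessments up to progression, for patients who progress and later respond: not clearly. The SAP defines progressive disease radiographically, and the sentence addresses a later response, not later stable disease.
- The response evaluable set (SAP 3.1.4): no. It uses clinical progression only to admit patients who have no post-baseline scan.
- Review of scenarios that Table 4 may not cover: no. Stable disease on or after Day 49 is already settled by the text.
- The statement that discrepancies with the protocol are inadvertent: no. It applies to SAP Section 2 only.

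**2. Can a scan follow clinical progression?** Yes. Table 9-1 has a discontinuation scan, and the SAP schedule runs on to radiographic progression. The new-therapy limb would often close the window, but Section 7 says data on subsequent anticancer treatment have not been required since 29 January 2020, so that limb may not be detectable for later patients.

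**3. Worked patients.** Days count from Cycle 1 Day 1. No new therapy or consent withdrawal is recorded. The SAP's Day 49 and 28-day rules are applied to both windows, so only the cut-off differs.

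| Course | Protocol window | SAP window | Changes |
|---|---|---|---|
| SD on an unscheduled scan Day 40, clinical progression Day 45, SD Day 56 | Day 56 excluded; only scan is before Day 49; BOR NE | BOR SD | DCR: no to yes |
| PR Day 56, clinical progression Day 70, PR Day 112 | PR unconfirmed; BOR SD | Second PR is 112 − 56 = 56 days later, at least 28; confirmed PR | ORR: no to yes; DCR yes in both |
| SD Day 56, clinical progression Day 80, SD Day 112 | BOR SD | BOR SD | None |
| No earlier scan, clinical progression Day 45, RECIST PD Day 56 | BOR NE | BOR PD | BOR category only |

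**4. Direction.** With the other limbs held the same, the earliest of a longer list of dates cannot be later than the earliest of a shorter list, so every scan in the protocol window is also in the SAP window. Under Table 4, extra later scans can turn NE into SD or confirm a response. They do not undo a confirmed response or a qualifying SD. ORR and DCR therefore rise or stay the same.

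**5. Scale.** An affected patient has a post-baseline scan, so given measurable disease at baseline the patient is in the response evaluable set under either window. The denominator n is unchanged and one patient moves a rate by 100/n points. SAP 2.3 gives six patients in the first cohort and a maximum of 36; the other sizes are for illustration.

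| n | Points per patient |
|---|---|
| 3 | 33.3 |
| 6 | 16.7 |
| 12 | 8.3 |
| 24 | 4.2 |
| 36 | 2.8 |

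With assumed counts and Clopper-Pearson 95% intervals: at n = 36, 26 against 25 successes is 72.2% (54.8 to 85.8) against 69.4% (51.9 to 83.7). At n = 6, 5 against 4 is 83.3% (35.9 to 99.6) against 66.7% (22.3 to 95.7).

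**The case against.** The strongest reply is that a radiographic rule is sound for endpoints declared to follow RECIST 1.1. Neither document defines clinical progression, and the SAP uses radiographic progression consistently in its scan schedule, BOR and PFS. Restoring the clinical limb for BOR alone would put BOR and PFS on different notions of progression. This stands as a reason why the SAP's rule may be preferred. It does not excuse leaving the change out of Section 7, where smaller changes are recorded.

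The second reply is that the route is narrow. A qualifying non-PD scan before clinical progression settles DCR the same way under both rules, and the protocol keeps scans made on the progression date itself. Protocol 11.3 asks for a post-treatment scan only after stopping for reasons other than PD, and 9.4 and 10.1 continue scans only in patients who have not progressed; whether a clinically progressed patient falls under these is unclear. A changed ORR needs a responding or confirming scan after clinical progression and before new therapy, which is remote. All of this stands, and it limits the likely size.

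Third, the endpoints are secondary and descriptive, with no formal test, and Part 2 will not be run. The planned summary of discontinuation reasons and the listing of tumor assessments may make affected patients traceable. That also stands, but a listing does not correct a summary rate or its stated definition.

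A reader might infer that the reported DCR and ORR are materially inflated, or that every patient stopped for clinical progression is misclassified. The documents support neither: they do not say how many patients stopped for this reason, and most orderings of scan and progression give the same result.

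**Conclusion.** The discrepancy is real and undeclared. "i) radiographic or clinical disease progression" in the protocol became radiographic progression alone in the SAP's BOR rule, nothing else in the SAP puts the clinical limb back, and the Section 7 statement that DCR keeps the CBR definition is not accurate for affected patients.

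DCR is the more exposed endpoint, because one non-PD scan on or after Day 49 is enough; ORR is affected only in the rarer confirmation case. The shift is upward or nil. Each affected patient is worth 2.8 points at n = 36 and 16.7 points in the first cohort, which matters because SAP 5.2.9.1 reports by dose level as well as overall. The total effect is unknown and may be zero. The conclusion assumes that the SAP is programmed as written and that some scans follow clinical progression without recorded new therapy or consent withdrawal. It is a departure from the protocol to be declared and shown, not evidence that the radiographic rule is wrong.

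**What to change.** Take one of two courses before database lock.

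1. Restore clinical progression to the first limb of the BOR rule in SAP 4.1.2.1, so that it matches protocol 12.3.2.
2. Keep the radiographic rule, list the change and its reason in Section 7, correct the statement that DCR has the CBR definition, and present BOR, ORR and DCR under both windows.

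The cost is a small amount of programming. Both courses need a recorded date of clinical progression, which the documents do not describe; if none was collected, the discontinuation date can serve as a stated proxy for patients whose reason was clinical progression. DCR may fall slightly under the protocol window. A later RECIST PD scan would also no longer set BOR to PD, and such a patient may become NE; this changes the BOR table but not ORR or DCR. The clinical limb is missing from the SAP's PFS data window too, also without a Section 7 entry, so the same entry should say which notion of progression each endpoint uses.

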9.4. Survival Follow-up Phase

Follow-up shall be attempted and documented for each patient that is in the long-term Survival Follow-up Phase at least once every 3 months. Follow-up can be via telephone, clinic visits, or by receiving information from a family member or another provider who is administering care. Patients will be followed for survival until at least 50% of the patients enrolled to Part 2 of the study have died. This will be considered the end of study. However, patients who are still receiving treatment at this time shall continue to receive study treatment until the criteria for study drug discontinuation are met.

The following information will be collected for all patients:

- Survival status
- Details of any anticancer treatment

For patients who have not had disease progression at the time of study drug discontinuation, tumor assessments should be performed every 8 weeks until the occurrence of progressive disease or study completion.

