Duration of Objective Response (DOR) is the time between first objective response of CR or PR and the first date that progressive disease is objectively documented or death. Patients who do not experience objective PD or death will not be included in the analysis.

Time to first objective response is the time from first dose of study drug to first objective response of CR or PR. Patients who do not experience objective response of CR or PR will be censored at the last adequate assessment date.

PFS is defined as the time (number of months) from date of first dose of study drug until date of documented disease progression or death due to any cause, whichever comes first. More specifically, PFS will be determined using all the assessment data up until the last evaluable visit prior to or on the date of (i) radiographic or clinical disease progression; (ii) withdrawal of consent to obtain scans; or (iii) receiving subsequent anticancer therapy, whichever is earlier. Death is always categorized as a confirmed PD event. Censoring methods for patients who do not experience PD or death will be described in the study SAP.

OS is calculated as the time (number of months) from date of first dose of study drug to the date of death due to any cause. Patients who do not experience fatalities during the course of the study will be censored at the date last known to be alive. Patients lacking data beyond the day of first dose of G1T38 will have their survival time censored at day of first dose. OS will not be censored if a subject receives other antitumor treatments after the study drugs.

The BOR, ORRs, and CBR and their corresponding 95% exact CIs will be calculated by Clopper-Pearson method. DOR, time to first objective response, PFS, and OS will be analyzed based on time-to-event summary method. For PFS and OS, Kaplan-Meier estimates will be plotted and tabulated at selected landmark time points (ie, 6 months, 1 year, 1.5 years, and 2 years).

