5.2.9. Efficacy Analyses

5.2.9.1 Analysis of Tumor Response

The number and percentage of subjects in each category of BOR according to programmatically-derived tumor response (CR, PR, SD, PD, or NE) based on investigator's measurements will be presented by dose level and overall. Also, the number and percentage of subjects in each category of BOR (Confirmed CR, Confirmed PR, SD, PD, or NE) based on CRF collected timepoint response (confirmed) will be summarized by dose level and overall. Similar analyses will be repeated for ORR and DCR.

Estimates of response rate, along with its associated exact 95% two-sided CIs using Clopper-Pearson method will be computed for ORR, BOR, and DCR within each treatment group.

The above analyses will be based on the RES. Analysis will be repeated for FAS based on programmatically derived BOR (confirmed) and DCR with additional category of Non-CR/Non-PR.

In addition to confirmed response (CR_{confirmed}, PR_{confirmed} and ORR_{confirmed}) in BOR summary, both confirmed response and unconfirmed response (CR_{unconfirmed}, PR_{unconfirmed}, and ORR_{unconfirmed}) will be presented in a separated BOR summary based on programmatically derived response for response evaluable population.

Detailed tumor assessment data from CRF will be listed together with derived response for target lesion(s) and derived time point response for all enrolled patients.

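### Both planned PFS analyses censor patients taken off drug for clinical or investigator-called progression unless RECIST PD is derived or a death is recorded; the likely bias is upward, and no planned analysis shows its size.

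*SAP*

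**What the plan says.** **Event definition.** SAP 4.1.2.1, under Progression-free Survival, states: "Progressive disease (PD) is defined as radiographical determined disease progression based on the criteria by RECIST Version 1.1". It continues: "PD status is derived from the radiographical assessments by investigators that have been entered to the EDC", and "A PFS event is defined as a PD event or a death due to any cause".

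**Censoring rules.** Tables 5-1 (primary PFS) and 5-2 (secondary PFS) have no row for clinical progression, and none for investigator-recorded PD that the program does not reproduce. Without derived PD or death, either table censors the patient at the last adequate radiological assessment. The primary analysis is meant to describe PFS up to treatment discontinuation; the secondary one adds scans after the last dose.

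**Reasons for stopping drug.** Protocol 11.3 lists among its triggers: "Patient has radiographically documented or clinically determined disease progression".

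**The investigator's own call.** SAP 4.1.1 says: "The overall response at each time point is also assessed by the investigators and is collected on eCRF". SAP 5.2.9.1 adds a BOR summary "based on CRF collected timepoint response (confirmed) will be summarized by dose level and overall" and repeats ORR and DCR in a similar way. SAP 5.2.9.3 gives PFS no such repeat.

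**Data cut-off.** Protocol 12.3.2 ends the data used for PFS and BOR at the earliest of several dates, the first being "i) radiographic or clinical disease progression". The SAP cut-offs for BOR and PFS mention RECIST progression only. SAP Section 7, which lists changes from the protocol, does not include this one.

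**The concern.** A patient whose physician judges the disease to have progressed, and who stops drug for that reason, has failed treatment in the ordinary sense. If the program finds no RECIST PD, Kaplan-Meier treats that patient as having left follow-up for reasons unrelated to prognosis and credits the patient with the experience of those still on treatment. The censoring happens because the patient appears to be doing badly, so it is likely informative and the expected direction is upward.

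PFS and 1-year PFS by investigator assessment are named secondary objectives of Part 1. Both planned PFS analyses use the same PD definition, so comparing them does not isolate the effect of this choice. ORR and DCR are shown both ways; PFS is not.

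**Working it through.** **1. Following the patient through the rules.** The documents give no figure for this point to reproduce, because Part 1 has no PFS target.

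- Clinical progression, drug stopped, no RECIST PD on any scan: the patient falls under no progression, or discontinuation for a reason other than progression. Either row censors at the last adequate scan in Table 5-1, and the matching rows do so in Table 5-2.
- Investigator's eCRF response is PD, derived response is SD: the outcome is the same, because PFS uses the derived status.
- Death recorded without PD: an event in both tables.
- A scan after the last dose shows PD: an event in the secondary analysis. It is doubtful that it counts in the primary one, given that analysis's stated aim.

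**2. Are such patients scanned again?** The passages do not agree.

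- SAP 4.1.1 continues scans to radiographic RECIST progression, withdrawal of consent to scans, or new therapy. Protocol 10.1 continues them to objective progression. Protocol Table 9-1 marks a tumor assessment at discontinuation.
- Protocol 9.4 continues off-drug scans "For patients who have not had disease progression at the time of study drug discontinuation", and 10.1 repeats that condition, without saying whether clinical progression counts as progression. Protocol 11.3 provides a Post-Treatment Visit scan, with conditions, only for stopping for reasons other than PD.

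**3. Size, as an illustration.** Inputs:

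- Median 10.1 months, from protocol 12.1. This was the assumption for the osimertinib arm of Part 2, which was not opened, and serves only as a scale.
- Scans every 8 weeks: 56/30.4375 = 1.840 months, so six scans by month 12, the sixth at 11.04 months.
- Share q of progressions that are clinical-only or discordant: not in the documents, assumed 10% to 30%.
- Exponential progression times, with radiographic PD found at the next scan.

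Hazard: λ = ln 2/10.1 = 0.06863 per month. Probability of progressing within one scan interval: p = 1 − exp(−0.06863 × 1.840) = 0.1186.

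*Counted as events when they occur:* S(12) = (1 − q) × exp(−11.04λ) + q × exp(−12λ) = (1 − q) × 0.469 + q × 0.439.

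*Censored at the last scan, with no later scan or death:* among those at risk at a scan, the Kaplan-Meier factor is (1 − p)/(1 − qp), so S(12) = [(1 − p)/(1 − qp)]^6. At q = 20% this is [0.8814/0.9763]^6 = 0.9028^6 = 0.541.

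| q | Counted as events | Censored, no later scan or death |
|---|---|---|
| 10% | 46.6% | 50.4% |
| 20% | 46.3% | 54.1% |
| 30% | 46.0% | 58.3% |

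A simulation of 400,000 patients gave 46.5%, 46.2% and 45.9% against 50.3%, 54.0% and 58.2%.

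**4. What shrinks it.**

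- Next scan shows PD in all of them: S(12) = exp(−11.04λ) = 46.9%, whatever q is (46.8% simulated). The bias nearly vanishes.
- Next scan shows PD in half, q = 20%: about 50%.
- No scan shows PD but all deaths are captured, with an assumed median of 6 months from clinical progression to death, q = 20%: the chance that such a patient is still alive at month 12 is 0.715, so S(12) = 0.8 × 0.469 + 0.2 × 0.715 = 51.8% (51.7% simulated).

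**The case against.** The best defence is that the SAP does what the objective asks. The objective is PFS from investigator assessments under RECIST v1.1, protocol 12.3.2 derives time point response by program, and clinical progression is not a RECIST criterion. That stands: the derived-RECIST analysis should stay as planned, and anything else is a sensitivity analysis.

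Three stronger readings are tempting and are not supported.

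- *The rules end these patients' scans.* SAP 4.1.1, the main rule in protocol 10.1 and the discontinuation scan in Table 9-1 point the other way. The passages conflict; they do not establish that scanning stops.
- *Deaths no longer catch these patients.* Death is an event in both tables. Protocol 10.6.1.10 asks for all deaths to be reported while the study is ongoing, even after a patient has left it. SAP Section 7 says overall survival data were not required from 29 January 2020, which makes capture of later deaths uncertain, not absent.
- *The SAP treats the same patients as failures elsewhere, or the dropped word creates the bias.* The clinical-progression limb of the response evaluable set (SAP 3.1.4) covers only patients with no post-baseline scan and only places them in a denominator. In protocol 12.3.2 clinical progression is a data cut-off; it is not named as an event. Removing it lets later scans count, which tends to reduce the bias. The missing Section 7 entry is a documentation gap.

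Discordance between program and investigator may also be uncommon, since non-target progression and new lesions are investigator entries. Some of the effect will be visible anyway: PFS tables give censoring reasons, disposition gives reasons for stopping, and efficacy data are listed by patient. Neither produces a PFS estimate with these patients counted.

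**Conclusion.** The gap in definition is real. Clinical-only progression, and investigator-recorded PD that the program does not derive, lead to censoring in both PFS analyses unless RECIST PD is later derived or a death is recorded. The censoring is likely informative and PFS is probably biased upward.

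A reader might infer that PFS is shown to be overstated by several points. The documents do not support that. In the illustration the excess in 12-month PFS runs from almost nothing, when the next scan shows PD in all of these patients, to about 12 percentage points (58.3 − 46.0) at a 30% share with no later scan or death. The share, the exponential model and the survival time after clinical progression are assumptions, and the median is borrowed from Part 2. Part 1 has at most 36 patients and no formal test, so no decision rule is affected. The point justifies a cheap addition to the analysis; the planned analysis need not be replaced.

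**What to change.** 1. In SAP 5.2.9.3, add a sensitivity PFS analysis in which the event is the earliest of derived RECIST PD, investigator eCRF overall response of PD, clinical progression recorded as the reason for stopping study drug (dated at that determination), or death. Present it beside the derived-RECIST analysis.
2. In the derived-RECIST analysis, state in Tables 5-1 and 5-2 how these patients are handled and give them their own censoring reason.
3. Reconcile the passages on whether tumor assessments continue after clinical progression: SAP 4.1.1 and the main rule in protocol 10.1 against protocol 9.4 and 11.3.
4. List in SAP Section 7 that clinical progression was removed from the PFS and BOR data cut-off.

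The cost is one extra table and a few sentences. The eCRF overall response is already collected. Whether the eCRF holds a date for clinical progression cannot be seen from the documents; if it does not, the SAP should say which recorded date is used. The drawback is that clinical progression is less objective than RECIST PD, which is why the two analyses should be shown together.
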